Aim 1: Determine the feasibility, acceptability, and adaptations of the CNA Wellbeing Program by conducting 8-week course in one NH with a goal of 15 CNAs, and up to 20 CNAs per NH. Evaluation will focus on a) participation (including home practice adherence); b) attendee evaluation of training; c) barriers/facilitators of participation; d) use and retention of session materials by participants; and e) recommendations for improvement.

Aim 2: Conduct a pilot test of adapted protocols and intervention in sample of 30 CNAs from 2 NHs to reexamine feasibility and acceptability. Evaluate fidelity and impact of training by measuring a) attendance, b) satisfaction with training, c) pre-post measures of self-compassion, intent to leave job, perceived stress, job satisfaction, burnout, and attitudes towards persons with dementia.

Interventions and Duration

Mindful Self-Compassion has been developed and validated in other populations as a course of eight 2.5- hour weekly sessions. A modified version of this program will be tested in Aim 2, which is also a validated version of the MSC program. This version is six, 1-hour weekly sessions. Each session begins with meditation, follows with discussion of previous week's home practice, introduction of main theme of session and new formal and informal practices. Each session will be offered in a location convenient to the NH, outside of work hours, at times convenient for participants, and offered at two different times to accommodate schedules.

Sample Size and Population

Eligibility to this study will include: Certified Nursing Assistant employed by participating nursing homes; over the age of 18; able to speak and write in English; works at NH 20 or more hours per week; expects to be employed with NH for the duration of the course; and expects to be able to attend 75% of the sessions. Up to 20 CNAs per NH will be able to participate, with a goal of 15 participants. If over 20 CNAs are interested, the study will enroll the 20 CNAs who score highest on the Screening Questionnaires' Perceived Stress Scale who are interested in participating.

STUDY TEAM ROSTER

RESEARCH TEAM			
Name	Role	Telephone	Email
[name], MPH	Principal Investigator	[contact]	[contact]
[name], MPH	Post Doctoral Fellow and Co-Principal Investigator	[contact]	[contact]
[name]	Co-Investigator, Evaluation and Research Design	[contact]	[contact]
[name]	Co-Investigator/Intervention Director		[contact]
[name]	Consulting Co-Investigator		[contact]

1 STUDY OBJECTIVES

This preliminary study will modify, refine, and test a MSC training intervention, to be known as CNA Wellbeing Program, for CNAs who care for nursing home residents. Our goal is to increase CNA coping skills and well-being, thereby reducing intent to leave the job, reducing burnout, and improving job satisfaction and attitudes toward people with dementia. The proposed research will be conducted in 3 similarly rated and structured community NHs.

1.1 Aim 1 Objective

Determine the feasibility, acceptability, and necessary adaptations of the CNA Wellbeing Program needed to meet the diverse cultural background, limited literacy, and job and family challenges of the nursing home CNA workforce, including the unique challenges of caring for persons with dementia, and of the data collection methods.

- A.** Conduct a field trial of the standardized 8-week CNA Wellbeing Program with 15 CNAs within a single community NH. Evaluation will focus on: (a) participation (including home practice adherence and attendance); (b) attendee evaluation of the training; (c) barriers to and facilitators of participation; (d) use and retention of session material by participants; and (e) recommendations for improvement of training.
- B.** Field test the feasibility and acceptability of our study recruitment and evaluation strategy.
- C.** Use data collected from the field test to modify recruitment strategies, protocols, and course structure, content and materials so as to be maximally feasible, acceptable and effective in a CNA population.

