1.2 Aim 2 Objective

Conduct a pilot test of the adapted protocols and intervention in a sample of 30 CNAs from 2 similarly rated and structured community NHs to reexamine feasibility and acceptability, identify trends in key intermediate and long-term outcomes, and estimate effect size in preparation for a future randomized trial.

- A.** Evaluate the fidelity and immediate impact of the modified training by measuring (a) training attendance; (b) satisfaction with the training; and (c) pre-and post-training measures of self-compassion, perceived stress, job satisfaction, job burnout symptoms, and attitudes towards persons with dementia.
- B.** Evaluate the sustained impact of the training by comparing baseline, 3-and 6-month post-training measurements of: intent to leave job, self-compassion, perceived stress, job satisfaction, job burnout symptoms, and attitudes towards persons with dementia.

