4.1 Inclusion Criteria

Participants must meet all of the following inclusion criteria to participate in this study:

- *Certified Nursing Assistant working at 3 participating NHs*
- *Works at least 20 hours a week (on average) with participating NHs*
- *Speaks and reads English*
- *Over 18 years old*
- *Intends to work with NH for the duration of the MSC course*
- *Expects to be able to attend a majority (75%) of the sessions*

If over 20 CNAs are interested in the course, and we are not able to accommodate all whom would like to participate, an additional inclusion criteria will be scores on the Perceived Stress Scale portion of the Screening Questionnaire (see Appendix D1). The 20 CNAs with the highest scores on the PSS will be eligible for the intervention course. As of the completion of this trial, this measure was unnecessary.

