6.1 Schedule of Evaluations

Measure	Pre-Course*	Course									3 Months	6 Months	
		1	2	3	4	5	6	7	8	9			
Feasibility Measures													
Attendance		X	X	X	X	X	X	X	X	X			
Attrition (Withdrawal)		X	X	X	X	X	X	X	X	X			
Audio Recording										X			
Screening Questionnaire (Demographics & PSS)	X												
Baseline Interview (JSS, Intent to Leave, ADQ, MBI, PSS, SCS, PROMIS)	X												
Weekly Questionnaire (PROMIS, Home Practice, Adverse Events)		X	X	X	X	X	X	X	X				
End-of-Program Interview (Acceptability Measure, JSS, Intent to Leave, ADQ, MBI, PSS, SCS, PROMIS, Adverse Events)									X	X			
3 Month & 6 Month Interview (JSS, Intent to Leave, ADQ, MBI, PSS, SCS, PROMIS, Adverse Events)											X	X	
Measures of Adverse Events and Safety Monitoring	Pre-Course*	Course									3 Months	6 Months	
		1	2	3	4	5	6	7	8	9			
PROMIS Depression Screen	X	X	X	X	X	X	X	X	X	X		X	X
Adverse Event Monitoring Form		X	X	X	X	X	X	X	X	X		X	X
Adverse Event Reporting Form					X				X			X	X
Nursing Home Level Data		2018			2019			2020					
Administrator Interview						X							
CMS NH Compare Website		X				X					X		
*Begins 2 weeks before onset of program													

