**Mindful Self-Compassion Training  
to Improve Retention, Job Satisfaction,  
and Attitudes toward Dementia among  
Long-Term Care Nursing Assistants:  
Certified Nursing Assistants' Wellbeing**

Analysis Overview. Analyses of the intervention’s effectiveness will primarily comprise tests of changes to the outcome measures (see below) from baseline at three post-baseline timepoints: (a) post-intervention, (b) a 3-month follow-up, and (c) a 6-month follow-up. All outcomes were recorded at the same time points within the same self-report survey. Thus, overall, with baseline there were four data collection time points in the study. Secondly, analyses will consider differences in effectiveness by comparing two intervention’s two approaches: (a) the 20-hour intervention delivered in one NH and (b) the 6-hour intervention delivered in two additional NHs. In addition to outcome analyses, participants’ univariate demographic and professional characteristics were calculated to describe the sample (not detailed). Missing data were not imputed, resulting in analyses using listwise deletion of participant observations without data at each time point and for each outcome. Statistical significance was set at  $p < 0.05$  throughout (two-sided) and all analyses were conducted in Stata 16.1.

Primary Outcome. The primary outcome in the study was *Change in Intent to Leave Job*. The specific question asked of participants was “How likely is it that you will leave this job in the next year?” with intent to leave specifically being defined as a “Somewhat likely” or “Very likely” response (1 = Yes) versus a “Not at all likely” response (0 = No). The analysis of the primary outcome proceeded in two steps. First, the descriptive frequencies and percentages of “Yes” and “No” response were calculated for all participants at all four data collection time points to summarize the primary outcome across participants and time. Second, tests for the statistical significance of change from baseline was determined using three sets of McNemar’s exact  $X^2$  tests compared baseline versus the three post-baseline time points. These tests were chosen as appropriate for the (a) non-parametric nature of the data and (b) paired nature of the comparison.

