Secondary Outcomes. There were nine secondary outcome domains in the study: (a) mean *Job Satisfaction Scale* (JSS) score; (b) mean *Approach to Dementia Questionnaire* (ADQ) score; (c) mean *Perceived Stress Scale* (PSS) score; (d) mean *PROMIS Depression Scale—Short Form* (PROMIS) score, (e) mean subscale *Maslach Burnout Inventory—Human Services Scale* (MBI) scores; (f) mean total and subscale *Self-Compassion Scale—Youth* (SCS) scores; (g) *Weekly Attendance*; (h) *Number of Days Per Week Spent in Out-of-Class Exercises*; and (i) mean *Satisfaction with Course* score. Briefly, the JSS measured how satisfied participants were with at their job and included 3 individual items (Range: 0–18); the ADQ measured participants’ attitudes toward NH residents with dementia and included 11 items (Range: 0–44); the PSS measured participants’ stress and included 10 items (Range: 0–40); the PROMIS measured participants’ depression levels and included 8 items (8–40); the MBI measured participants’ burnout and included 20 items; the SCS measured participants’ self-compassion and included 17 items; and the study-created *Satisfaction with Course* measure evaluated course-specific satisfaction and included 8 items. Rather than having a total score measuring burnout, the MBI featured 3 subscales related to *Depersonalization*, *Emotional Exhaustion*, and *Reduced Personal Accomplishment* constructs all with a range of 0.0–6.0. The SCS, meanwhile, featured a total score measuring self-compassion along with six subscales related to *Self-Kindness*, *Self-Judgment*, *Common Humanity*, *Isolation*, *Mindfulness*, and *Over-Identification* constructs all with a total range of 1.0–5.0. All scales and sub-scales were summed into unweighted composites of individual items. *Satisfaction with Course* items all had five response options ranging from “Strongly disagree” (1) to “Strongly agree” (5). *Weekly Attendance* was defined as “% of intervention classes fully attended” with a possible score from > 0.0% to 100.0%. Meanwhile, *Number of Days Per Week Spent in Out-of-Class Exercises* was defined as “mean # of days per week over the course of the intervention spent out-of-class doing course mindfulness exercises” with a range from 1.0 to 7.0. The analysis of the secondary outcomes proceeded in three steps. First, the descriptive frequencies, percentages, means, and standard deviations of all measures were calculated for all participants at all four data collection time points to summarize the

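### The protocol makes recruitment and evaluation feasibility an aim and records attrition, but the SAP analyses no recruitment yield, withdrawal or interview completion, and its participation figures appear to leave out enrolled CNAs with zero attendance or practice

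*Protocol*

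**What the plan says.** Protocol section 3 describes a one-arm feasibility trial that prepares for a later randomised trial. Section 1.1 gives Aim 1B as "Field test the feasibility and acceptability of our study recruitment and evaluation strategy", and Aim 1C says what the results are for: "Use data collected from the field test to modify recruitment strategies, protocols, and course structure, content and materials". Section 1.2 says that the Aim 2 pilot is "to reexamine feasibility and acceptability, identify trends in key intermediate and long-term outcomes, and estimate effect size".

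The schedule in 6.1 has a Feasibility Measures block. Beside attendance it has a row that begins "Attrition (Withdrawal", marked at each of the nine course sessions. Sections 6.2.1 and 9.1 describe interest sheets and Screening Questionnaires with pre-printed ID numbers. Section 6.2.1 states a goal of 15 CNAs per home.

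Two of the eligibility criteria in 4.1 concern expected participation: "Expects to be able to attend a majority (75%) of the sessions" and "Intends to work with NH for the duration of the MSC course".

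The SAP says that its effectiveness analyses "will primarily comprise tests of changes to the outcome measures". Intent to leave is primary. It then states: "There were nine secondary outcome domains in the study". These are six questionnaire scales, attendance, days of home practice and course satisfaction. Attendance is the percentage of classes attended in full, on a range that starts above 0%. Home practice is a mean number of days per week, on a range of 1.0 to 7.0. Missing data are handled by listwise deletion at each time point and for each outcome.

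**The concern.** A feasibility study should tell the designers of the next trial how many CNAs can be recruited, how many stay, and how many can still be interviewed six months after the course. The protocol makes this an aim and collects most of what is needed, but the SAP does not turn it into a result. Retention is a real uncertainty here. Section 2 cites average annual CNA turnover of 65%, and section 5.1 has each participant in the study for about 8 months.

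The participation figures that the SAP does plan are also selective. If CNAs who enrolled and then attended no class are left out, the mean describes attenders only. If feasibility is then judged for the CNA workforce, which is how Aim 1 is framed, the figure also rests on people who said beforehand that they expected to come.

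**Working it through.** The documents give no recruitment rate, retention rate, feasibility threshold or sample-size derivation, so there is no planned figure to reproduce. The planned numbers agree with each other: 15 + 30 = 45 = 3 × 15.

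**Step 1. Aims against planned analyses.**

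| Protocol item | Analysis in the SAP |
|---|---|
| Aim 1A: participation, including home practice | Attendance; days of home practice |
| Aim 1A: attendee evaluation of the course | Course satisfaction |
| Aim 1B: recruitment | None |
| Aim 1B: evaluation strategy | None (no interview completion, no account of missing data) |
| 6.1: attrition | None |
| Aim 2: feasibility re-examined | Only the three outcomes listed under Aim 1A |

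The protocol has no analysis section of its own to fill the empty rows.

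**Step 2. The floor of the participation scales.** Protocol 5.3 keeps following participants whatever their adherence, so a CNA can be enrolled, attend nothing and remain in the study. Such a person scores 0%, which lies outside the SAP's attendance range. Someone averaging less than one day of practice per week lies outside the practice range.

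Let *a* be mean attendance among those above zero and *w* the share of enrolled CNAs at zero. The mean over all enrolled is *a* × (1 − *w*). Both inputs are assumptions:

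- *w* = 0: no change.
- *w* = 2/15, *a* = 75%: 0.75 × 13/15 = 65.0%.
- *w* = 2/15, *a* = 85%: 0.85 × 13/15 = 73.7%.

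The same factor, 13/15 = 0.867, applies to mean days of practice if 2 of 15 practised on no day and were left out.

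**Step 3. Selection at entry.** The attendance criterion means expecting to attend 0.75 × 8 = 6 of 8 sessions, or 0.75 × 6 = 4.5, so in practice 5 of 6. CNAs who expect to attend less would probably attend less, so the likely direction is upward relative to the workforce. The size depends on how many were turned away on this criterion and what they would have attended. The documents give neither.

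**Step 4. What a retention result could support.** Exact (Clopper-Pearson) 95% limits for *x* retained of *n* are the 2.5% quantile of Beta(*x*, *n* − *x* + 1) and the 97.5% quantile of Beta(*x* + 1, *n* − *x*). With assumed retention:

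| Retained | One home (n = 15) | 6-week version (n = 30) |
|---|---|---|
| 60% | 9/15: 32.3–83.7% | 18/30: 40.6–77.3% |
| 80% | 12/15: 51.9–95.7% | 24/30: 61.4–92.3% |
| 90% or just above | 14/15: 68.1–99.8% | 27/30: 73.5–97.9% |

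These intervals do not measure an error in the plan. They show the precision that a report from this sample could claim.

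**The case against.** Several counter-arguments have weight.

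- **Aim 1 is largely formative.** Questionnaires, interviews and group feedback feed the revision of the course, and section 10.3 shows that feedback from the first home changed the reimbursement. This stands, but qualitative feedback does not replace counts of those recruited, withdrawn and interviewed.
- **Numbers followed up can be read from planned tables.** The SAP tabulates outcomes at all four time points, so the denominators will be visible. This stands in part. Those denominators mix withdrawal, missed interviews and unanswered items, and no account of who is missing is planned.
- **The protocol plans a survey comparing participants with other CNAs in the home (5.1).** It covers stress and demographics, not recruitment yield, and the SAP does not analyse it.
- **The scale ranges may be loose wording.** They may be. The SAP should then say that zeros are included.
- **For a later trial with the same eligibility rule, attendance among eligible CNAs is the relevant figure.** This stands, provided recruitment yield is reported beside it.

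A reader might infer more than the documents support. One inference is that eligibility removes CNAs who cannot attend. The criterion is the CNA's own expectation, not inability. Another is that the attendance figure is shown to be inflated by a known amount. The number screened out is not given and could be zero. Section 4.1 says that the rule for more than 20 interested CNAs proved unnecessary, which, read literally, means that no home exceeded 20. A reader might also want attendance per interested CNA. That would count people never offered the course as non-attenders and mix reach with adherence. Finally, the SAP sentence on tests of change concerns effectiveness analyses. It does not rank effectiveness above feasibility.

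**Conclusion.** The omission is plain from the text and rests on no assumption. Aim 1B, the feasibility part of Aim 2 and the attrition record have no planned analysis of recruitment yield, withdrawal or interview completion. For a feasibility trial this is more than missing detail, because the SAP as written cannot answer a stated aim.

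The bias point is narrower. The attendance and home-practice figures appear to exclude enrolled CNAs at zero, and they describe only CNAs who expected to attend 75% of sessions. Taken alone, they are likely to overstate feasibility for the workforce. The size cannot be computed from the documents. The fall from 75% to 65% holds only if 2 of 15 enrolled CNAs attended nothing and were left out. If nobody enrolled was at zero and nobody was screened out, there is no overstatement from these sources.

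**What to change.** Add a feasibility section to the SAP, reported by nursing home and by course version:

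1. A participant-flow table: interested, screened, enrolled (against the goal of 15 per home), withdrawn, and interviewed at End-of-Program, 3 months and 6 months. Give exact 95% confidence intervals for the proportions, and reasons for ineligibility where they were recorded.
2. Attendance and home practice over all enrolled CNAs, with zero attendance and zero practice counted as 0 and the stated ranges changed to start at 0.
3. Recruitment yield beside those figures, and a statement that the feasibility conclusion rests on items 1 to 3.

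The cost is a little more analysis and SAP wording. Interest sheets, screening forms, consents, withdrawal records and interviews should supply the main counts. The protocol describes no log of ineligibility reasons, so that line may be incomplete and should say so. The attendance figure may become less favourable.

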1.2 Aim 2 Objective

Conduct a pilot test of the adapted protocols and intervention in a sample of 30 CNAs from 2 similarly rated and structured community NHs to reexamine feasibility and acceptability, identify trends in key intermediate and long-term outcomes, and estimate effect size in preparation for a future randomized trial.

- A.** Evaluate the fidelity and immediate impact of the modified training by measuring (a) training attendance; (b) satisfaction with the training; and (c) pre-and post-training measures of self-compassion, perceived stress, job satisfaction, job burnout symptoms, and attitudes towards persons with dementia.
- B.** Evaluate the sustained impact of the training by comparing baseline, 3-and 6-month post-training measurements of: intent to leave job, self-compassion, perceived stress, job satisfaction, job burnout symptoms, and attitudes towards persons with dementia.

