3 STUDY DESIGN

This is a single-arm feasibility trial that will refine an existing MSC intervention in preparation for a future, randomized controlled trial with the primary goal of improving CNA job retention. We will recruit 15 CNAs from a single nursing home (NH), pilot the 8-week intervention, and collect feedback via questionnaires, interviews and a semi-structured focus group at the end of the course. Data from this cohort will be used to refine study protocols and course structure/materials for maximum feasibility and acceptability. A refined intervention will subsequently be tested in 30 CNAs from two NH settings (15 CNAs per home), with pre, post, and follow-up measurements of stress, burnout, self-compassion, job satisfaction, attitudes towards dementia, and intent to leave their job.

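### Aim 2 promises an effect size for the later randomised trial, but a single-arm pilot yields only before-after change, which is a biased basis, of unknown direction, for sizing that trial

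*Protocol*

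**What the plan says.** Protocol section 1.2 gives Aim 2 several purposes. One is to "estimate effect size in preparation for a future randomized trial", from a planned 30 nursing assistants in two homes who take the adapted course. Section 3 is open about the design: "This is a single-arm feasibility trial that will refine an existing MSC intervention in preparation for a future, randomized controlled trial", the later trial being described "with the primary goal of improving CNA job retention".

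Under Analysis Overview, the SAP's main analyses are "tests of changes to the outcome measures (see below) from baseline at three post-baseline timepoints". For intent to leave, the primary outcome, it uses McNemar "tests compared baseline versus the three post-baseline time points". Continuous scales get Wilcoxon signed-rank tests. The one comparison between groups sets the 20-hour course against the 6-hour course; both are active and they ran in different homes.

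The SAP's descriptive step gives frequencies, percentages, means and standard deviations at all four time points, for all participants together. Results are split by course only for PSS, PROMIS and total SCS. The SAP names no effect-size statistic, no SD of change and no correlation between visits. Neither document says how the promised effect size would enter the later trial's sample size.

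**The concern.** A randomised trial tests the difference between arms. A single arm gives the change in people who took the course, and that change is the course effect plus whatever would have happened to the same people without it. The second part could be a drift over time, a response to repeated interviewing, or a worsening under job strain. No one in this study is followed without the course, so the two parts cannot be separated. The staff-meeting survey in Protocol section 5.1 does reach other nursing assistants, but no repeat is stated, so it gives no control change.

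A larger sample or a confidence interval would not help, because the issue is which quantity is estimated, not how precisely. If the before-after figure were carried uncorrected into a sample-size calculation, the later trial would be the wrong size. Preparing that trial is the pilot's stated purpose, so this bears on what the pilot can deliver.

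**Working it through.** The documents contain no power, effect-size or sample-size calculation, so there is no stated figure to reproduce. What follows is an illustration.

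**Inputs.** The two-sided 5% level is taken from the SAP and applied to the later trial. Everything else is assumed: 80% power, a before-after change of 0.5 SD, a range of control-arm changes, individual randomisation, and a normal approximation with equal arms.

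**Step 1: size the trial on the before-after change.**
n per arm = 2(1.960 + 0.842)² / d² = 2 × 7.849 / 0.25 = 62.8, so 63. (A t-test calculation gives 64.)

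**Step 2: recompute power at the true between-arm effect.**
True effect = 0.5 × (1 − c), where c is the control-arm change as a share of the observed change.
Power = Φ(true effect × √(63/2) − 1.960), with √(63/2) = 5.612.

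| Control change, c | True effect (SD) | Power at 63 per arm | n per arm for 80% |
|---|---|---|---|
| worsen by 25% | 0.625 | 94% | 41 |
| none | 0.500 | 80% | 63 |
| improve by 20% | 0.400 | 61% | 99 |
| improve by 25% | 0.375 | 56% | 112 |
| improve by 50% | 0.250 | 29% | 252 |

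For example, at c = 0.25: 0.375 × 5.612 − 1.960 = 0.145, and Φ(0.145) = 0.56. The pattern does not depend on 0.5: at 0.3 or 0.8 SD, c = 0.25 again gives 56% and c = 0.5 gives 29%.

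**Step 3: repeat for a binary outcome, since intent to leave is yes/no.** Suppose intent to leave falls from 50% to 30%. A two-proportion calculation gives 93 per arm.

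| Controls end at | Power at 93 per arm | n per arm for 80% |
|---|---|---|
| 55% | 94% | 61 |
| 50% | 80% | 93 |
| 45% | 56% | 163 |
| 40% | 30% | 356 |

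A 5-point fall in controls is 25% of the 20-point change, and the power agrees with Step 2.

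**Step 4: scale, for the continuous outcomes only.** The term effect size is undefined. With equal SDs at both visits, the SD of change is SD × √(2(1 − r)), where r is the correlation between visits. Change divided by its own SD is therefore d / √(2(1 − r)), which is 0.85, 1.00, 1.29 or 1.58 times d at r = 0.3, 0.5, 0.7 or 0.8. If a true d of 0.5 were entered on that scale as though it were a difference in post-course scores, the trial would have 88, 63, 38 or 26 per arm and 91%, 80%, 59% or 44% power. Analysing change scores in the later trial would keep power at about 80%. The mismatch can go either way, and r is not in the documents.

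**The case against.** The strongest reply is that nothing shows the later trial would be too small. A reader might infer from the missing control arm that it would probably be underpowered. That requires controls to improve, and the documents give no control change. Some features make overstatement plausible: participants volunteer, outcomes are unblinded self-report, and listwise deletion may drop people who have left the job. Others point the opposite way. Choosing the most stressed applicants, the clearest source of regression to the mean, was not needed (Protocol 4.1). Eligibility required an intention to stay for the length of the course, which may lower intent to leave at baseline and let it drift upward. With annual turnover put at 65% in the Protocol's background, untreated staff could well worsen. This part of the reply stands, and it is why the direction is left open.

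A reader might also infer that the sponsor has committed to sizing the trial on this figure. Section 1.2 does not say so, and the harm is conditional on that use. Whether attention and weekly texts belong to the effect depends on a comparator that is not named; against usual care they would be part of it. The SD at each visit is already planned. These replies narrow the point but do not remove it: the aim still offers a quantity for the randomised trial that this design cannot identify.

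**Conclusion.** The point holds in a limited form. Before-after change from one arm is not the between-arm effect, and Aim 2 offers it as preparation for a trial that needs the latter. As a basis for sizing, it is biased in an unknown direction. If controls shared 20% to 25% of an observed change, a trial sized for 80% power would have about 56% to 61%. With no control change it would keep 80%. If controls worsened by 25% of the change it would have about 94% and be larger than needed.

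These figures rest on assumed effects, an assumed 80% target and uncorrected use of the pilot figure. They show sensitivity and do not predict what will happen. There is a further gap: the primary outcome is summarised over both courses together, so the SAP plans no separate estimate of intent to leave for the 6-week course that Aim 2 is about.

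**What to change.** 1. In Protocol section 1.2, replace the effect-size purpose with wording such as: *estimate, for the 6-week course, the SD of change, the baseline-to-follow-up correlation, the proportion with 3- and 6-month data, and the frequency of intent to leave at each visit, for use in planning a later randomised trial.*
2. In the SAP's descriptive step, add the SD of change and the correlation with baseline. Show these, the SDs already planned and the intent-to-leave frequencies separately for the 6-week course.
3. State in the SAP and in the report that before-after change is descriptive and will not by itself serve as the treatment effect in the later trial's sample size. That calculation should rest on a smallest worthwhile difference between arms.

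Protocol section 4.1 refers to the trial as complete, so item 3 matters most: it limits how the existing result may be used. The cost is some wording and a few extra table columns from data already collected. The sponsor gives up a pilot effect size as a headline planning figure.
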